## 8. Risks

a. Medical risks, listing all procedures, their major and minor risks and expected frequency.

There are no significant medical risks involved in this study. This study falls in the category of "research not involving greater than minimal risk," described by federal regulations as "the risks of harm anticipated in the proposed research are not greater considering probability and magnitude, than those ordinarily encountered in daily life or during the performance of routine physical or psychological examinations or tests." Research in this category includes: "...confidential survey research that collects identifying information, with or without sensitive information."

This study will involve the use of surveys and receipt of text messages. All participants will be informed

that participation in the study is completely voluntary and will be reminded that they can decide not to answer any question on the brief survey and that they can stop participating at any time. Potential risks for participants who participate in this study include distress related to the research study (e.g., personal nature of questions asked). While the study will attempt to preserve patient confidentiality, there is potential for breaches of confidentiality, but minuscule given the limited number of personnel with access to participant information. It is also possible that by promoting father engagement, the intervention could increase friction between parents and/or other key caregivers that could also result in distress and/or conflict. However, past perinatal research focused on father involvement suggest that programs to enhance maternal-paternal relationships actually improve maternal mental health outcomes and has not found harms associated with father-mother relationships as a result of greater father involvement. We have developed a monitoring plan to assess for these issues and resources to refer participants as needed.

b. Steps taken to minimize the risks.

Human subject approval has been granted for prior formative work and pilot feasibility testing of this research protocol by the Johns Hopkins institutional review (IRB00117690) that has informed the current protocol. Significant attempts will be made to minimize risks to participants.

The research team on this project has training and experience in the protection of human research participants and the treatment of protected health information as evidence by completion of their institutional compliance courses that are reviewed every 3 years per Johns Hopkins Medicine faculty and staff requirements. New staff without prior training must complete human subjects training through the Johns Hopkins Committee on Clinical Investigation courses as a part of orientation training and as a condition of their employment. All research staff who will conduct assessments and introduce program materials will also be trained about how to interact with participants in sensitive ways and watch for signs of distress during survey administration. Research staff will be supervised to ensure that they are following specified procedures.

Regarding participant assessments, we do not anticipate medical risks to the participant related to completing study assessments. If a participant shows any sign of significant psychological distress, they will be referred to the primary investigator or to the emergency department for further evaluation and management. Participants in our pilot research did not display or report discomfort or distress as a result of assessment procedures.

We have developed a monitoring plan to specifically assess fathers' and mothers' distress as a parent and perceptions of caregiver conflict between the father and other caregivers over the course of the study. We will assess all participants in the baseline and follow-up surveys and assess all mothers and intervention fathers at 2-month intervals using text message queries of abbreviated measures. Any participant with an affirmative response will be provided resources/hotlines about supporting partner relationships, reducing stress, and mental health, including the Hopkins' Division of MFM's Social Work team. The monitoring approach is as follows:

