**Figure 1. Overview of Study Procedures**

**Table 1. Schedule of Activities**

	pre-screening Pre- consent)	(Visit 1/ Time 1)	(Visit 2/ 2 months)	(Visit 2/ 4 months)	(Visit 3/ 6 months)	(Visit 2/ Time 2/ 7 months+/ weeks)
Review eligibility (phone/in-person)	X					
Informed consent (phone/in-person)		X				
Demographics/background characteristics		X				
Outcome evaluation						
Parent knowledge, self-efficacy, behavior survey		X				X
Intervention acceptability survey						X
Monitoring responsive texts			X	X	X	
Randomization		X				
Control & Experimental Interventions – Text4Father		X	X	X	X	
Adverse Events Reporting		X	X	X	X	X

**Setting.** We will conduct this study and recruit participants in Baltimore. Baltimore is a community with marked health disparities related to maternal and infant outcomes. In 2015 in Baltimore, the infant mortality rate was almost 2 times higher for black (9.7/1,000 live births) than white infants (5.4/1,000); this rate was 1.3 times greater than Maryland's rate, and 12% of babies born were low birthweight versus a national average of 8%. Settings will include the Hopkins Maternal-Fetal Medicine (MFM) Clinic and Fetal Assessment Center where we successfully collaborated for the 6-week feasibility pilot that informs this proposal. [name], Professor and Director of the Johns Hopkins' Division of MFM, facilitated MFM staff education for the pilot and is committed to ensuring this project's feasibility. The Center sees over 21,000 fetal ultrasound exams and delivers over 2,400 babies each year. The majority of patients are publicly insured (62%) and half are African American. Based on our preliminary work, we estimate that 865 infants each year will have first-time lower income fathers.

**Participants and Recruitment.** Research staff will recruit 120 adult expectant fathers and their female partners (120 pregnant females) (60 dyads per study arm) from the Hopkins' MFM Clinic and Fetal Assessment Center to be enrolled through 25 weeks gestation. The index participant and their partner will contact study staff to be scheduled for a research visit. An eligibility screener will be individually completed with both members of the dyad to determine study eligibility. Our target is to have complete data on 48 dyads so we set sample size at 60 in order to account for attrition.

[figure not shown]

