We will use SMS services through a licensed commercial provider such as EngageSpark, TextNow, or RapidSMS for communicating with father and mother participants in all arms of the study. Each of these companies allow for texting and calling and can be enabled for use on a phone, tablet, or computer that makes this platform optimal for this study. Further, each of these companies has strict policies to protect the user to prevent unauthorized disclosure of information and physical, electronic, and procedural safeguards are in place according to industry standard procedures and security procedures. Research staff will be responsible for monitoring fidelity of the texts sent and using the online account to register and send any interim text-message to participants in the study. Since a telephone number is created with each account, the telephone number will be recognizable to participants as Text4Father communication.

Finally, all participants will be encouraged to use standard safety mechanisms such as a pin or password to lock access to their cell phones by others, if not already in place.

**Control Groups.** The usual care arm will receive 3 interim texts (1 text each at 2 months, 4 months, and 6 months) that will assess distress and perceptions of caregiver conflict between the father and other caregivers. The usual care arm will not receive any additional interaction since maternity care typically does not provide any organized educational approach.

For ethical reasons all arms will receive at baseline a new parent handout about local birth resources/hotlines.

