R=Reporter; FR=Father report; MR=Mother report; WCC=Well-child care; T1=Time 1; T2=Time 2; AAP=Am Academy of Pediatrics

b. Study duration and number of study visits required of research participants.

The study will last 7 months. Participants will be recruited through 25 weeks of gestation and followed 2 months after the infant's birth. For fathers who meet the study criteria and consent to participate in the study, they will complete two study visits: a survey at baseline and another at 7-month follow up; fathers assigned to the Text4Father in the interim will receive approximately two texts a week for 7 months. For mothers who meet the study criteria and consent to participate in the study, they will complete two study visits: a shorter survey at baseline and another at 7-month follow up. All study participants (fathers and mothers) will receive text at the beginning a flyer jpeg about the study to share with their partner and 3 interim texts (1 text each at 2 months, 4 months, and 6 months) that will assess distress and perceptions of caregiver conflict between the father and other caregivers.

c. Blinding, including justification for blinding or not blinding the trial, if applicable.

This will not be a blinded study. The intervention consists of receiving text messages which, by definition, is a non-blinded activity.

d. Justification of why participants will not receive routine care or will have current therapy

stopped.  
Not applicable.

e. Justification for inclusion of a placebo or non-treatment group.  
Not applicable.

f. Definition of treatment failure or participant removal criteria.  
For the purposes of this behavioral study, treatment failure is not applicable. Criteria for participant removal: if system error from text messaging platform indicates that a participant's cell phone number is no longer active and we are unable to contact participants' shared contacts after no more than 3 attempts with each contact in the first 10 days that is repeated no more than twice thereafter.

g. Description of what happens to participants receiving therapy when study ends or if a participant's participation in the study ends prematurely.  
Participation in this study will not impact participants' usual care regardless of how the study ends or if a participant's participation in the study ends prematurely.

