**For father participants**

- At baseline, all fathers will receive a new parent resource handout, including birthing support groups and resources/hotlines to support relationships, stress, and mental health, and study contact information to reach out at any point to study team members for assistance.
- Fathers will receive additional interval texts that will query him on the following:  
Q1. How's your relationship with your partner (better, same, worse)?  
Q2. How's your relationship with other caregivers in your infant's life (better, same, worse)?

Q3. Becoming a father can be stressful. Would it help you to talk to somebody for support (yes, no, unsure)?

Any father who answers “worse” to Q1 and/or Q2, or “yes” or “unsure” to Q3 will be provided contact information for the Hopkins Division of MFM’s Social Work team and the study team, and a weblink that will host resources/hotlines that address stress/mental health and relationship supports.

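### The protocol both sends and does not send the interim distress and conflict texts to control fathers, and caregiver conflict, part of a risk it names, has no clear by-arm analysis

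*Combined protocol and SAP*

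**What the plan says.** **Interim texts.** Five places in the combined protocol and SAP bear on who gets the distress and conflict queries.

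- Section 4, Control Groups: "The usual care arm will receive 3 interim texts (1 text each at 2 months, 4 months, and 6 months"), covering distress and caregiver conflict. It then adds: "The usual care arm will not receive any additional interaction".
- Section 4, item b (study duration and visits), applies to everyone enrolled: "participants (fathers and mothers) will receive text at the beginning a flyer jpeg about the study to share with their partner and 3 interim texts", at the same three time points and with the same content. No arm is excluded.
- Section 8, item b (monitoring plan): "We will assess all participants in the baseline and follow-up surveys". The same sentence goes on to say staff will "assess all mothers and intervention fathers at 2-month intervals using text message queries of abbreviated measures".
- Section 8, For father participants: "Fathers will receive additional interval texts that will query him on the following". No arm is stated. The preceding bullet, on the handout, does cover everyone: "At baseline, all fathers will receive a new parent resource handout".
- Schedule of Activities: the row "Monitoring responsive texts" is marked at 2, 4 and 6 months, without separating the arms.

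**Caregiver conflict.** Section 8, item a, accepts that the intervention might cause friction between the parents or with other important caregivers. The Measures Table has a 12-item caregiver conflict scale, reported by father and mother, and lists it only under moderator factors. The Surveys text in Section 4 and the data descriptions at the end of the data sharing plan show that it is collected from both parents, in all arms, at baseline and follow-up. In Section 7 it appears only among the exploratory moderators. That subsection ends with an exploratory by-arm comparison of maternal and infant outcomes, which it does not list.

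**The concern.** Section 4 and Section 8 give control fathers different treatment, and the two places that could settle the matter (the father bullets and the schedule) state no arm. Texting control fathers departs from the monitoring plan. Not texting them departs from two statements in Section 4. The control condition is also affected, because the Control Groups paragraph presents these texts as the contact that arm has and rules out anything further.

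If the monitoring plan is followed, father-reported distress and conflict between baseline and follow-up would be detected in one arm only. Referral information would likewise be triggered in one arm only. Any interim comparison of fathers by arm would then reflect how the data were obtained as well as any effect of the intervention.

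The second issue is separate. The protocol names a possible harm, measures it in both arms, and then gives the follow-up measurement no clear by-arm analysis. A trial meant to inform a larger one could finish without an estimate of whether the intervention raises conflict with other caregivers.

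**Working it through.** **1. Scheduled interim queries under each version.** Inputs from Section 7: 120 fathers and 120 mothers, 60 couples per arm. From Section 4: three texts per person.

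| | Section 4 (Control Groups; item b) | Section 8 (monitoring plan) |
|---|---|---|
| Mothers, both arms | 120 × 3 = 360 | 120 × 3 = 360 |
| Intervention fathers | 60 × 3 = 180 | 60 × 3 = 180 |
| Control fathers | 60 × 3 = 180 | 0 |
| Total | 720 | 540 |

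The whole difference, 720 − 540 = 180, is the control fathers. Under Section 8, the fathers scheduled for interim queries are 60 in the intervention arm and 0 in the control arm. These are scheduled recipients; the number who answer would be smaller.

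**2. Can the versions be read together?** Reading the Control Groups paragraph as meaning control mothers only does not help, because item b of Section 4 names fathers and sets no arm limit. The father bullets use an all-inclusive term for the handout but not for the texts, whereas the mother bullets use one for the texts. That pattern is compatible with the Section 8 restriction, so the restriction cannot simply be dismissed as a slip.

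**3. Is caregiver conflict compared by arm anywhere?**

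- Primary and secondary outcomes (Measures Table): not listed. Partner relationship quality, by contrast, appears twice, as a baseline moderator and as a follow-up secondary outcome, so the plan does give one scale both roles elsewhere.
- Aim 3 models (Section 7): fitted to study outcomes, which this scale is not.
- Maternal and infant outcomes comparison (Section 7): does not cover the father report and does not clearly cover the mother report.
- Study Reports (Section 8): pooled over arms.
- Friction between the parents themselves is compared by arm, through cooperative coparenting (primary) and partner relationship quality (secondary). The gap concerns other caregivers.

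**4. How precise would a by-arm estimate be?** The plan expects 20% loss: 60 × 0.80 = 48 per arm, which matches its target of complete dyads. For a baseline-adjusted difference in SD units, with baseline to follow-up correlation r,

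half-width of 95% CI = 1.96 × √[(2/n)(1 − r²)].

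| n per arm | r = 0.3 | r = 0.5 | r = 0.7 |
|---|---|---|---|
| 48 (plan) | 0.382 | 0.346 | 0.286 |
| 40 (assumed) | 0.418 | 0.380 | 0.313 |

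For example, at n = 48 and r = 0.5: 1.96 × √(0.04167 × 0.75) = 0.346. With the t quantile on 93 df the first row becomes 0.387, 0.351 and 0.289. The values of r and the 40 per arm are assumptions; the documents give neither.

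Without baseline adjustment, at 48 per arm the half-width is 1.96 × √(2/48) = 0.40 SD. The difference detectable with 80% power at an assumed two-sided 5% level is (1.960 + 0.842) × √(2/48) = 0.57 SD. This supports reporting an estimate with its interval and not a test.

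**The case against.** **The contradiction is only a drafting slip.** Section 8 does not say that only those groups are texted, so texting every father would breach no express prohibition. It is true that the exclusion is an inference. But it comes from a single sentence that sets all participants (surveys) against all mothers and intervention fathers (texts), and there is no other natural reason to name the intervention fathers. The passages need to be reconciled either way.

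**The texts are not the control arm's sole contact.** Control participants also get the baseline handout, the flyer message and two surveys. That is correct. The point about the control condition is limited to the interim period.

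**The consequence is small.** All fathers receive the handout with support resources and study contacts, everyone is surveyed twice, and mothers are texted in both arms. One of the mothers' questions asks about the father's relationship with other caregivers, so that part of the risk is queried in both arms whichever section governs. This stands, and it confines the imbalance to fathers' interim answers and the referrals that follow from them.

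**The caregiver conflict point is a preference.** The study is classed as minimal risk, conflict is handled by monitoring and referral, and no by-arm harm analysis is promised. Classing the scale as a moderator is indeed not an error in itself. But the risk is one the protocol names, and the data are already collected in both arms.

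**The intervals assume a different model.** Aim 3 plans random-intercept models of change. For a simple difference in change among 48 completers per arm, 1.96 × √[(2/48) × 2(1 − r)] gives 0.47, 0.40 and 0.31 SD for r = 0.3, 0.5 and 0.7. That is wider, and it strengthens the case for keeping the analysis descriptive. The figures in the working apply to the baseline-adjusted analysis recommended here.

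**Conclusion.** The concern holds on both parts and should be put right, though it does not threaten the trial's main comparisons.

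The sections conflict on whether control fathers receive three interim queries each or none, and nothing else in the document resolves it. This conclusion needs no assumption beyond the natural reading of the Section 8 sentence. If Section 8 is followed, interim ascertainment and referral among fathers are one-sided.

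Caregiver conflict is not missing as data; what is missing is a clear by-arm analysis. The gap is certain for the father report. For the mother report it depends on whether the maternal outcomes comparison in Section 7 was meant to include it. The estimate would have modest precision, 0.29 to 0.38 SD either side with 48 per arm under the assumed correlations, which is useful for planning a larger trial but not for ruling a small harm in or out.

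**What to change.** 1. Reconcile Section 4 (Control Groups and item b), Section 8 (monitoring plan and father bullets) and the Schedule of Activities row so that one rule for control fathers is stated throughout. The documents do not show which rule is intended, and none is proposed here.
2. Name follow-up caregiver conflict, father-reported and mother-reported, as a descriptive harm outcome. Report the baseline-adjusted difference between arms with a 95% CI for each reporter. Keep baseline caregiver conflict as the moderator.
3. State in Section 7 whether the maternal and infant outcomes comparison includes the mother-reported scale.
4. If interim answers are tabulated by arm, use only data obtained in the same way in both arms.

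The pooled format of the ongoing Study Reports need not change. The cost is protocol wording and two models, one per reporter, on data already planned.

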**For father participants**

- At baseline, all fathers will receive a new parent resource handout, including birthing support groups and resources/hotlines to support relationships, stress, and mental health, and study contact information to reach out at any point to study team members for assistance.
- Fathers will receive additional interval texts that will query him on the following:  
Q1. How's your relationship with your partner (better, same, worse)?  
Q2. How's your relationship with other caregivers in your infant's life (better, same, worse)?

Q3. Becoming a father can be stressful. Would it help you to talk to somebody for support (yes, no, unsure)?

Any father who answers “worse” to Q1 and/or Q2, or “yes” or “unsure” to Q3 will be provided contact information for the Hopkins Division of MFM’s Social Work team and the study team, and a weblink that will host resources/hotlines that address stress/mental health and relationship supports.

### For mother participants

- At baseline, all mothers will receive a new parent resource handout, including birthing support groups and resources/hotlines to support relationships, stress, and mental health, and study contact information to reach out at any point to study team members for assistance.
- All mothers will also receive interval texts that will query her on the following:

Q1. How’s your relationship with your partner (better, same, worse)?

Q2. How’s your partner’s relationship with other caregivers in your infant’s life (better, same, worse)?

Q3. Becoming a mother can be stressful. Would it help you to talk to somebody for support (yes, no, unsure)?

Any mother who answers “worse” to Q1 and/or Q2, or “yes” or “unsure” to Q3 will be provided contact information for the Hopkins Division of MFM’s Social Work team and the study team, and a weblink that will host resources/hotlines that address stress/mental health and relationship supports.

If participants reveal that they or their children are currently being abused or harmed in any way, or this is suspected, steps will be taken to ensure their safety, which may include contacting local authorities (e.g., law enforcement, child protective services). If participants exhibit behaviors that indicate they may hurt themselves or others, steps will be taken to ensure their safety, and the participant will be referred for appropriate psychiatric evaluation, as is standard medical practice.

As previously noted, all participants will provide informed consent and will be informed that their participation in the study will have no effect on subsequent medical care, that their study participation is voluntary, reminded they can choose not to answer any item, and can stop participating at any time. All patient data will be kept confidential and secure.

Due to the longitudinal nature of this study, we will collect tracking information from participants. We will assign a unique identification number to each participant as they enter the study that will allow us to link data over time and to their partner. We will maintain a separate database from participant response data that links a participant’s unique identification number to personal tracking contact information and to their partner to ensure integrity of participants’ identification number across time. This master list will be kept on a password protected computer in the PI’s locked office. All other data will be non-identifiable. All identifying information will be destroyed using paper shredders upon completion of the study.

The research team will manage data and maintain records for all collected data including data checking, cleaning, coding and entering. Standard security procedures will be followed, including use of password protection and secure daily backup and storage locations. We will develop a database management system for all collected data that will be confidential, accurate, and secure to house all data. Data will be collected and stored within JHU’s secure, institutionally managed REDCap survey and research database platform. Data transferred for additional analysis will take place within JHU’s virtual cloud storage and analysis platform (SAFE Desktop) that maintains HIPAA security standards. Use of a computer-based survey platform will minimize data entry errors and missing data. The data manager will perform weekly systematic protocols for data cleaning, and check for consistency and completeness (e.g., skip pattern error, duplicate or inconsistent responses).

**Data Safety Monitoring Plan.** The study will employ a data safety-monitoring plan consistent with NIH guidelines. [name] will be responsible for monitoring and handling adverse events and will assume responsibility for the ethical integrity of the proposed work. All investigators and research staff will meet weekly and a portion of these meetings will be dedicated to communicating about ethical issues related to the study, including patient safety, changes in risk/benefit ratio, and regulatory issues.

The PI will review the safety and progress of the study on an ongoing basis. Enrolled participants will be monitored throughout the study for untoward incidents (e.g., “Adverse Events”) occurring during the study. Study Reports will be generated focusing on subject recruitment, retention, and adverse events (AEs) that will give an in-depth synopsis of (1) study accrual; (2) reason for dropouts from the study; (3) whether all participants met entry criteria; (4) whether continuation of the study is justified on the basis that additional data are needed to accomplish the stated aims of the study; and (5) conditions whereby the study might be terminated prematurely. The PI and co-Investigators will conduct regular monitoring for enrollment rates, study data acquisition, and safety events, as a part of continuous oversight to comply with human subject safety requirements.

